- Percent change in Fractional Excretion of Calcium (FECa) from baseline (Screening visit) to the final day of treatment (Day 6 or the last measurement while on encaleret). FECa calculated using fasting blood levels and spot urine collection.
- Change in blood iPTH comparing average baseline iPTH to average peak iPTH on encaleret. The average baseline iPTH will include all baseline iPTH levels from the screening visit, Day -1, and pre-dose on Day 1. The average peak iPTH will average the peak iPTH levels on every day the patient is on encaleret (days 1 to 5). An increase in iPTH will be considered clinically significant if there is an increase both by 50% AND by more than 10 pg/dL.
- Change in 1,25-(OH)₂ Vitamin D on encaleret comparing the maximal level prior to receiving calcitriol (On Days 3-5) to baseline (Average of Day 1 Pre-dose levels). Increase will be considered significant if there is an increase of more than 50%. Participants who receive calcitriol prior to Day 3 will be excluded.
- Pharmacodynamic endpoints measured over 5 days of encaleret therapy:

- Blood iPTH – Absolute levels and change from baseline
- Albumin-corrected blood calcium – Absolute levels and change from baseline
- Ionized Calcium – Absolute levels and change from baseline
- Urinary calcium clearance (fractional excretion and 24-hour total excretion) – Absolute levels and change from baseline
- Serum levels of 1,25-(OH)₂ Vitamin D – Absolute levels and change from baseline
- Blood intact FGF23 (iFGF23) and C-terminal FGF23 (cFGF23) – Absolute levels and change from baseline
- Urine cAMP and citrate – Absolute levels and change from baseline
- Blood bone resorption marker, collagen cross-linked C-telopeptide (CTX) – Absolute levels and change from baseline
- Blood bone formation marker, blood procollagen type 1 N-propeptide (P1NP) – Absolute levels and change from baseline
- PK parameters such as maximum plasma concentration (C_{max}), time to maximum plasma concentration (t_{max}), apparent terminal half-life (t_{1/2}).
- Change in components of urine including: supersaturation, sodium, potassium, calcium, magnesium, chloride, phosphorus, sulfate, citrate excretion, oxalate, pH, uric acid, creatinine, osmolality, ammonium, urea nitrogen, protein catabolic rate

Study Population: Enrollment up to 30 male or female participants to achieve 15 to enter the treatment phase. Two cohorts:
Cohort 1: Permanent PSH (>1 year after surgery) with minimum of 7 and up to 10 participants

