24-Hour urine: Ca, Mg, PO4, Cr, Na, K, pH, Citrate Supersaturation Panel	Days -1 to 5 0-24 hrs (Start collection after first morning void and end 24 hours later) Day -1 and Day 5

Table C: Blood Sampling Days -1 to 5

Day -1: Baseline fasting labs including CBC, acute care panel, intact PTH, Ca, PO4, Mg, Cr, albumin, K, CK, Research blood, Bone turnover markers (CTX, P1NP), 25-(OH) Vitamin D, 1,25-(OH)₂ Vitamin D, cAMP, ionized calcium, TSH, FT4

		-30 min	-15 min	30 min	1 hour	2 hour	4 hour	12 hour	16 hour	24 hour
Day 1	Mineral labs	X	X	X	X	X	X	X	X	
	Safety Labs		X					X		
	Ionized Calcium		X				X	X	X	
	Research Blood	X	X			X	X	X	X	
	Bone Turnover Markers		X							
	1,25D	X	X							
	cAMP		X							
	Pk		X			X	X			
Day 2-4	Mineral labs		X	X			X	X	X	
	Safety Labs		X					X		
	Ionized Calcium		X				X	X	X	
	Research Blood		X				X	X	X	
	Bone Turnover Markers		X							
	1,25D		X							
	cAMP		X							
	Pk		X							
Day 5	Mineral labs		X	X	X	X	X	X	X	X
	Safety Labs		X					X		
	Ionized Calcium		X				X	X	X	X
	Research Blood		X			X	X	X	X	X
	Bone Turnover Markers		X							
	1,25D		X							X
	cAMP		X							X
	Pk		X			X	X			

Mineral Labs: Intact PTH, Ca, PO4, Mg, Cr, Albumin

Safety Labs: Acute care panel (Na, K, Cl, CO₂, BUN, Cr, eGFR), CK

Research Blood

Bone turnover Markers: CTX, P1NP

1,25-(OH)₂ Vitamin D, cAMP

a

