Encaleret (molecular formula $(C_{29}H_{33}ClFNO_4)_2 \cdot H_2SO_4 \cdot H_2O$, molecular weight 1144.15) is formulated as 4.5, 9, 27 and 54 mg film-coated tablets. Each tablet contains 5, 10, 30, and 60 mg of encaleret sulfate (CLTX-305), respectively. The active agent inhibits the CaSR, via allosteric modulation, with an IC_{50} of 86.2 ± 6.2 nM (in cell-based assays at 2 mM extracellular calcium). In humans, two major glucuronide metabolites (M1 and M3) occur. M1 ($IC_{50} > 3000$ nM) is inactive and M3 ($IC_{50} 67.3 \pm 6.6$ nM) is active.

Encaleret is rapidly absorbed in humans (t_{max} median 1.5 hr. (range 0.75–3 h at most single doses or at steady-state). The elimination half-life ($t_{1/2}$) was approximately 6.5 hours after single doses and 11–14 hours at steady state (14 days). Dose-proportional increases in plasma encaleret concentrations were documented over the encaleret sulfate dose range (5, 15, 30, 50 and 100 mg) in the fasted state without significant food effect. Encaleret showed minimal accumulation when administered once daily (QD) for two weeks in Japanese postmenopausal women. Based on non-clinical data, fecal excretion was the main route of elimination. In humans, excretion of unchanged encaleret and metabolites into urine was minimal ($< 5\%$ as total of parent and metabolite).

The two major glucuronide metabolites showed similar pharmacokinetics as the parent drug, with M1 median t_{max} approximately 2 hr. and M3 median t_{max} approximately 1.5 hr. For M1 (inactive), concentrations in plasma were approximately 2-fold higher than those of parent drug; M3 (active) concentrations were low (10% compared to parent). Neither M1 nor M3 showed prolonged elimination.

No significant age-related or race differences (US population vs. Japanese subjects) were observed in encaleret pharmacokinetics. AUC and C_{max} values may be approximately 37% and 30% higher in females but these differences were not significant when body weight was taken into account. Hepatic and renal impairment studies have not been conducted. In a drug interaction study, co-administration with ketoconazole, a potent CYP3A4 inhibitor, resulted in approximately 1.67x increase in C_{max} and approximately 2x increase in AUC₀₋₂₄ with slightly less effect on M1 and M3.

For additional information see Investigator's Brochure (IB), Section 4.3 and Section 5.2.

Mineral Effects of Encaleret in Prior Clinical Trials

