During the prior development program in osteoporosis, dose-related increases of endogenous serum parathyroid hormone (PTH) and blood calcium (Ca) were observed in subjects with presumed normal CaSR function (i.e., healthy volunteers and postmenopausal women with osteoporosis).

In healthy postmenopausal women, repeat encaleret sulfate doses of 15 or 20 mg resulted in consistent elevations in intact PTH (iPTH) over 3–4 hours after single daily dosing. Encaleret

sulfate dosing in phase 2 studies of normocalcemic subjects was limited to 15 mg once daily (QD) to minimize hypercalcemia.

With chronic once-daily dosing of encaleret sulfate up to 15 mg, albumin-corrected blood calcium (cCa) levels reached a plateau with up to 30% of subjects registering an elevated blood calcium above the upper limit of the laboratory reference range during long-term trials in postmenopausal women with normal systemic calcium homeostasis (normal CaSR sensitivity, normal parathyroid tissue). Such hypercalcemia was asymptomatic, modifiable by decreasing calcium/vitamin D supplementation, and/or resolved after stopping encaleret dosing. No serious adverse events (SAEs) related to either hyper- or hypocalcemia were observed in the encaleret program for osteoporosis in postmenopausal women (See IB Section 5.2).

In phase 1 osteoporosis trials, urinary calcium excretion decreased rapidly with encaleret, however, the effect only persisted for the first 12 hours. With once daily doses of 5 mg to 30 mg, 24-hour urinary calcium after 14 days of therapy was overall slightly increased (See IB Table 15 & 16, Figure 34). However, fractional excretion of calcium was lower than placebo at the 0-6 hour and 6-12 hour timepoints but elevated at the 12-24 hour timepoint. This suggests that the urinary calcium effect only persists for up to 12 hours and supports the use of every 12-hour dosing for maximal and sustainable urinary calcium effect. On the highest dosage of encaleret of 30 mg daily, despite blood calcium elevation above 11 mg/dL, urinary fractional excretion of calcium during the first 12 hours was suppressed. This suggests that encaleret may reduce urinary calcium excretion even during concomitant elevated blood calcium, supporting the hypothesis that encaleret has promise as a treatment for postsurgical hypoparathyroidism.

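### Daily iPTH peaks are not comparable across Days 1-5: the 1 h and 2 h draws exist on Days 1 and 5 only, so peaks on Days 2-4 are recorded as equal or lower

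*Combined protocol and SAP*

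**What the plan says.** The Synopsis (section 1.1) and the table in section 3 compare an average baseline iPTH with an average on-drug peak: "The average peak iPTH will average the peak iPTH levels on every day the patient is on encaleret (days 1 to 5". A responder rule is attached: "An increase in iPTH will be considered clinically significant if there is an increase both by 50% AND by more than 10 pg/dL". The same lists include iPTH level and change from baseline over the five treatment days.

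The draw times are in Table C (section 1.3). iPTH belongs to one panel: "Mineral Labs: Intact PTH, Ca, PO4, Mg, Cr, Albumin". That panel has eight crosses on Day 1 ("Day 1 Mineral labs X X X X X X X X") and five on each of Days 2-4 ("Day 2-4 Mineral labs X X X X X"). The empty cells on Days 2-4 include 1 h and 2 h. Research blood is also not drawn at 1 h or 2 h on Days 2-4, so no stored sample can fill the gap.

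Section 2.2 gives a median drug tmax of 1.5 h (range 0.75-3 h). It also says that, in healthy postmenopausal women, repeat doses of 15 or 20 mg encaleret sulfate "resulted in consistent elevations in intact PTH (iPTH) over 3–4 hours after single daily dosing". Section 9 has no rule for unequal sampling.

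**The concern.** A maximum depends on when one looks. Three of the five averaged peaks come from days with no scheduled look between 30 min and 4 h, which is where the documents place the drug's own peak. If iPTH follows the drug, the recorded peak on Days 2-4 understates the real one.

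Two readings could be affected. A steady response could appear weaker mid-week and recover on Day 5. A participant with some residual gland function could also fall below the 50% and 10-unit rule because of the draw times. The second matters most in Cohort 2, which is included to see whether strong stimulation can raise PTH in recovering glands. It has at most 5 participants, so one changed classification is 1/5 = 20 percentage points.

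**Working it through.** The documents state no expected change, SD or power for this endpoint, so there is no figure to reproduce.

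**1. Scheduled draws (Table C)**

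| Day | Post-dose iPTH times | Number |
|---|---|---|
| 1 | 30 min, 1, 2, 4, 12, 16 h | 6 |
| 2-4 | 30 min, 4, 12, 16 h | 4 |
| 5 | 30 min, 1, 2, 4, 12, 16, 24 h | 7 |

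Table B places the evening dose after the 12 h draw, so the 16 h draw is about 4 h after it. On Days 2-4 no nominal time lies 0.75-3 h after either dose. With the ±20 min window printed in Table B, a late 30 min draw could reach 50 min (0.83 h), just inside the lower edge.

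**2. Direction.** The Day 2-4 times are a subset of the Day 1 times. A maximum over a subset cannot exceed the maximum over the full set, so the recorded peak is equal or lower.

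**3. Size with summed-dose curves (assumed shapes, no noise).** Each dose adds g(t) proportional to exp(-ke·t) - exp(-ka·t), scaled to a single-dose peak of 1 and summed over 12-hourly doses. One rate constant is set by a half-life of 1, 2, 4, 6.5 or 8 h. The other is solved from ln(ka/ke)/(ka-ke) = time to peak. Loss = 1 - (five-day average peak as scheduled) / (same average with 1 h and 2 h also drawn on Days 2-4).

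| Assumed iPTH time to peak | Loss in the average peak rise |
|---|---|
| 0.5 h | 0% |
| 0.75 h | 0-1.5% |
| 1 h | 2.8-10.3% |
| 1.5 h | 7.7-19.0% |
| 2 h | 7.4-15.5% |
| 3 h | 1.5-2.6% |
| 4 h | 0% |

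The range for peaks at 1-2 h is thus about 3-19%. Two examples, both peaking at 1.5 h:

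- Half-life 2 h: daily peaks 0.96, 0.70, 0.70, 0.70, 0.98, a dip and rebound from a constant response.
- Half-life 8 h: 1.13, 1.29, 1.36, 1.37, 1.56, with no dip relative to Day 1.

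At a 1.5 h peak and half-lives of 1-4 h the loss is 12.5-19.0%. A rise that the fuller schedule would record as 11 becomes 11 × 0.810 = 8.9 to 11 × 0.875 = 9.6, below 10. (The threshold is printed in pg/dL here, and the PTH-Clamp rise in pg/mL; the example needs only that both numbers share a unit.)

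**4. Size with narrow pulses and no carry-over.** f(t) = (t/tp)^k · exp(k(1 - t/tp)), with tp = 1, 1.5, 2 h and k = 2, 3, 4. Average = (2 × Day 1/5 maximum + 3 × Day 2-4 maximum)/5.

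- Mildest (tp 1, k 2): (2 × 1.000 + 3 × 0.680)/5 = 0.808 of the true peak. The true rise needed to exceed 10 is 10/0.808 = 12.4.
- Most severe (tp 1.5, k 4): (2 × 0.833 + 3 × 0.178)/5 = 0.440. The rise needed is 10/0.440 = 22.7.

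The loss is 19-56% against the true peak. Against what the Day 1/5 schedule itself would record, the worst case is 1 - 0.440/0.833 = 47%.

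**5. Noise only, no response.** The expected maximum of k independent normal values is 1.029 SD (k = 4), 1.267 SD (k = 6) and 1.352 SD (k = 7). The planned average exceeds a plain baseline mean by (1.267 + 3 × 1.029 + 1.352)/5 = 1.14 within-day SD. With Days 1 and 5 at the six shared times, the excess is 1.27 SD.

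**The case against.** The strongest counter-argument is that the timing evidence comes from another setting. The 3-4 h elevation was seen with 15-20 mg sulfate once daily in women with presumed normal parathyroid function. Here each dose is 3 × 60 = 180 mg sulfate, 9 to 12 times as much, given twice daily, and section 2.2 puts the drug's half-life at 6.5 h after single doses and 11-14 h at steady state. A sustained iPTH response is plausible and would shrink the loss. With half-lives of 11-14 h in the summed-dose model it is 1.4-5.3% for peaks at 1-2 h. The most severe narrow pulse has only 6% of its peak left at 4 h. This stands, and it makes the size conditional.

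A reader might infer that peaks on Days 2-4 must be lower and that a false dip and rebound is certain. The schedule supports only equal or lower. A reader might also infer that the endpoint is biased downward overall and hides responders. That is not shown either: setting daily maxima against a mean baseline pushes the change upward by about 1.14 within-day SD under noise alone, and no within-day SD is given with which to net the two effects. Nor does the plan specify a test for a trend in daily peaks, so a reading of tolerance would be an informal misreading, not a planned result.

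Replacing the five-day average outright would also be hard to defend. It would cut five peaks to two, although section 3 gives averaging as the protection against spurious excursions. It would also follow PTH results that section 2.3.1 already reports for the first 6 participants of this open-label study.

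**Conclusion.** The asymmetry is certain from Table C, and so is its direction: equal or lower recorded peaks on Days 2-4. Its size rests on an assumed iPTH curve, because the documents give no iPTH time to peak in PSH at this dose. If the peak is at about 1-2 h and has faded by 4 h, the average peak rise loses roughly 3-19% under summed-dose curves and up to about 56% under narrow pulses. If the peak is near 0.5-0.75 h or 3-4 h in the summed-dose model, the loss is 0-3%. The net bias of the endpoint is not established.

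Severity is minor. The endpoint is exploratory, section 2.2 expects little PTH effect in PSH, and the primary FECa analysis does not use these peaks.

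**What to change.** Keep the five-day average as planned and add two rules to section 9.4.9:

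- Also report the average peak, and the 50% and 10-unit classification, from Days 1 and 5 only, using the post-dose times that both days share (30 min, 1, 2, 4, 12 and 16 h). Flag each participant whose classification differs between the two versions.
- For any day-to-day iPTH comparison, use only the post-dose times drawn every day (30 min, 4, 12 and 16 h).

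No new draws are needed; the cost is a little more analysis. The added version rests on two peaks instead of five and has slightly more noise inflation (about 1.27 against 1.14 within-day SD). Participants who stop before Day 5, which section 6.1.2 allows, would contribute Day 1 only. For these reasons it should sit beside the planned average and not replace it.

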6.1.2 Dosing and Administration

On Day -1/-2, participants who met eligibility criteria at the screening visit will be admitted to the NIH CC. Participants will not take their magnesium and potassium citrate starting on the morning of Day -2. Participants will not take their standard-of-care calcium or calcitriol starting on the morning of Day -1, and will instead start a personalized calcium supplementation, determined by investigators from their baseline calcium requirements and levels. They will start on a dietary daily calcium intake of approximately 1000 mg per day, which may be adjusted if needed.

Encaleret 162 mg twice a day will be administered to participants on Day 1 to 5. Additional calcium and/or calcitriol will be administered per algorithm (Table D) if required.

Calcium and calcitriol supplementation will be adjusted following the algorithm delineated in Table D with the primary goal of safety. Mild to moderate symptomatic hypocalcemia at any calcium level, cCa < 7 mg/dL, or borderline QT prolongation, would cause investigators to give oral calcium and/or calcitriol. Doses will be determined at the discretion of experienced investigator's understanding of the patient's prior supplement requirements and severity of hypocalcemia. IV calcium may be used for participants with severe hypocalcemic symptoms or QTcF > 500 ms. If a patient develops mild hypercalcemia, then calcium and calcitriol will be held until cCa is less than 9 mg/dL. If cCa has not trended down by 12 hours (or earlier per investigator discretion), encaleret will be stopped. If cCa is > 12 mg/dL, encaleret will be discontinued and calcium and calcitriol will be held until cCa is < 9 mg/dL, when home regimen is restarted.

On Day 3, investigators will add calcitriol supplementation if the albumin-corrected calcium remains < 8.5 mg/dL. The calcitriol dose will be determined by investigators, taking into account the current calcium level and the subject's baseline requirements.

The last dose of encaleret will be given on the night of Day 5. The patient will then resume calcium and calcitriol and be discharged home. If the patient is hypercalcaemic or hypocalcemic, their baseline calcium and calcitriol may be adjusted at discharge. If needed, they may remain at the NIH clinical center until their labs have stabilized to a safe level.

Table D: Titration algorithm:

		Encaleret Titration	Calcium supplementation titration*	Calcitriol titration*	Additional interventions/ monitoring

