Participants who develop abnormal clinical or laboratory assessments that indicate continuation of the treatment may put the subject at risk, may have their encaleret dosing interrupted at the discretion of the principal investigator.

Participants who met specific achievement thresholds for both the primary and secondary endpoints may be eligible for early drug discontinuation at the discretion of the principal investigator. The defined thresholds are as follows: The primary endpoint will be considered achieved if the fasting FECa has decreased by >40%. The secondary endpoint will be considered achieved if the participant has achieved concomitant normal or high blood calcium and normal urinary calcium. This approach aims to facilitate the evaluation of the PK-PD relationship (exploratory endpoint) during encaleret withdrawal.

Calcium and calcitriol supplementation and encaleret dose will be adjusted following the algorithm delineated in Table D with the primary goal of safety.

Drug Administration

Encaleret will be dispensed by the NIH Pharmacy. It will be provided as film-coated tablets containing the active ingredient encaleret provided in 54 mg dosage strength. Participants will receive encaleret 162 mg (3 tablets) every 12 hours per protocol with water.

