Day -2 or Day -1 (Admission): Participants will be admitted to the NIH CC either the day prior to dosing or two days prior to dosing based on subject convenience. All participants will be instructed to stop taking calcitriol and home calcium dosage, with last doses on Day -2. Participants on magnesium or potassium citrate will be instructed to stop these supplements, with last doses on Day -3. Calcium supplementation with calcium carbonate(500 mg elemental calcium) three times a day will start on Day -1. Baseline 24-hour urine will be opened the morning of Day -1, and fasting laboratory assessment will be obtained. Attempts will be made to collect fasting calcium levels prior to the morning calcium dosage, however, calcium will be given to participants if clinically indicated (for example, in the setting of hypocalcemia).

Days 1 to 5: Encaleret 162 mg BID will be taken orally by the patient. Detailed summary of planned calcium and calcitriol therapy is presented in Figure 2 and a dosing algorithm is presented in Table D. Frequent blood and urine sampling for 24-hours will be performed for safety and outcome measures (see [Table A and Table B](#)). Encaleret will be administered in the morning and evening with water approximately 12 hours between each dose. The last dose of study medication will occur on the evening of Day 5. Daily ECG will be performed for monitoring of QT interval.

Day 6 (Discharge): After the blood sampling is collected on the morning of Day 6 and the 24-hour urine is closed, all participants will resume their prior conventional treatment regimen. During Day 6, cCa levels will be monitored until the patient is discharged. This admission can be extended if additional monitoring or treatment (e.g., to stabilize calcium) is needed prior to discharge.

Follow-up:

Outpatient testing done on day 8-12 (Less than 7 days after expected discharge from the NIH clinical center) will be collected either at the NIH CC or local laboratory. Blood samples collected will be evaluated for blood creatinine, albumin, calcium, magnesium, phosphate, and PTH. A telephone contact to the patient will be conducted once calcium results are available to be reviewed with investigative team. Additional outpatient testing to follow up safety issues will be performed as needed.

An additional two telephone contacts will be performed at 30-days (\pm 7 days) and 90-days (\pm 7 days) after the last encaleret dose for screening of AEs and pregnancies, respectively.

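### The exploratory 1,25-(OH)2 vitamin D endpoint sets a maximum of a response-dependent number of draws against a mean baseline, which biases the apparent rise upward

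*Combined protocol and SAP*

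**What the plan says.** The tertiary endpoints in Section 1.1, repeated in the Section 3 table, define the 1,25D change by "comparing the maximal level prior to receiving calcitriol (On Days 3-5) to baseline (Average of Day 1 Pre-dose levels"). On size, the text reads "Increase will be considered significant if there is an increase of more than 50" percent. It does not say whether that threshold applies to each participant or to the group. On exclusions: "Participants who receive calcitriol prior to Day 3 will be excluded".

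Three other places fix how many values can enter the maximum.

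- **Draws.** "Table C: Blood Sampling Days -1 to 5" (Section 1.3) schedules 1,25D twice before the first dose on Day 1 (-30 and -15 minutes), once pre-dose on each of Days 2 to 4, and on Day 5 both pre-dose and at 24 hours.
- **Scheduled calcitriol.** Section 6.1.2: "On Day 3, investigators will add calcitriol supplementation if the albumin-corrected calcium remains < 8.5 mg/dL". Table A marks this start on Days 3, 4 and 5.
- **Early stopping.** Section 6.1.2: "Participants who met specific achievement thresholds for both the primary and secondary endpoints may be eligible for early drug discontinuation". Table D also stops encaleret for some hypercalcemia. Section 7.1 then returns the participant to active vitamin D, which ends the eligible draws.

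No analysis method is given for this comparison. Section 9.4.9 says only that mixed models might be used for the pharmacodynamic variables.

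**The concern.** Two features of the rule work together. First, the on-treatment side is the highest of several noisy values and the baseline side is an average, so noise alone produces an apparent rise. Second, the number of values is not fixed by design. It depends on when calcitriol starts, which depends on calcium on study drug, and on whether encaleret is stopped early. Two participants with the same 1,25D behaviour can have different chances of passing 50% because their calcium differed.

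At stake is the conclusion on 1-alpha hydroxylase, which is a named exploratory objective. With at most 15 treated participants, a few chance crossings could colour it. The plan is aware of this kind of problem for iPTH: it averages the daily peaks so that stray values do not drive the result. The 1,25D row next to it in Section 3 uses a single maximum and gives no justification.

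**Working it through.** **Plan's own figure.** None exists for 1,25D. The power figures in Section 9.2 concern FECa only and do not bear on this point.

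**Step 1. Count the eligible draws (Table C with Section 6.1.2).**

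- Calcitriol starts on Day 3: about one (Day 3 pre-dose; the hour of the calcitriol dose is not stated).
- Starts on Day 4: two.
- Never needed: three pre-dose draws, or four if the Day 5 24-hour draw counts. The text does not say whether it does.
- Encaleret stopped early: fewer, and none if stopped before the Day 3 draw.

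**Step 2. Model.** Assumptions: no drug effect; log-normal independent noise with log-scale SD σ = √ln(1 + CV²). The documents give no CV, so 10% to 30% is shown. The statistic is R = max(k on-treatment draws) / mean(2 baseline draws), and a crossing is R > 1.5.

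**Step 3. Hand checks at CV 20%** (σ = √ln 1.04 = 0.198).

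- Mean change, one draw: about CV²/2 = 0.04/2 = 2%, from dividing by a noisy baseline.
- Mean change, three draws: the expected maximum of three standard normals is 3/(2√π) = 0.846, so about 0.846 × 20% + 2% = 19%.
- Crossing, one draw, with the two baseline draws acting as one: 1 − Φ(ln 1.5 / (√2 × 0.198)) = 1 − Φ(0.4055/0.280) = 7.4%.

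Simulation gives 2.0%, 19.6% and 7.3%, in agreement.

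**Step 4. Simulated results, no drug effect.** Figures move by 0.1 to 0.2 points between runs.

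| CV | Mean change, 1 / 3 draws (independent baseline draws) | Crossing 50%, 1 / 3 draws (independent baseline draws) | Crossing 50%, 1 / 3 draws (baseline draws act as one) |
|---|---|---|---|
| 10% | +0.5% / +9% | 0.0% / 0.1% | 0.2% / 0.6% |
| 15% | +1% / +14% | 1.2% / 3.4% | 2.7% / 6.8% |
| 20% | +2% / +20% | 4.4% / 11.3% | 7.3% / 16.7% |
| 25% | +3% / +25% | 8.2% / 20.0% | 12.2% / 25.9% |
| 30% | +5% / +32% | 11.8% / 27.5% | 16.4% / 33.2% |

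At CV 20% with independent baseline draws, two draws give 8.1% and four give about 14.2%. The two Day 1 draws are 15 minutes apart, so the last column may be the nearer one.

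**Step 5. Correlated days.** With one effective baseline and a correlation of 0.7 between adjacent days that decays with distance (assumed), Days 1 and 3 correlate at 0.7² = 0.49. The one-draw chance at CV 20% is 1 − Φ(0.4055 / (0.198 × √(2 × 0.51))) = 2.1%, and three draws give 7.4%. The levels fall but the gap between one and three draws remains.

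**Step 6. With a true 25% rise.** At CV 20% and independent baseline draws, 22% cross with one draw and 45% with three. Draw count alone doubles the apparent response.

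**Step 7. Scale.** At CV 20%, 15 participants with three draws each would give 15 × 0.113 = 1.7 chance crossings on average, against 15 × 0.044 = 0.7 with one draw each.

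**Step 8. Exclusion.** Assume CV 25%, a true mean rise of about 20%, and the lowest 20% by calcium dropped. The single-draw crossing rate, all against retained, is 28.9% against 31.7% if calcium and 1,25D responses correlate at +0.5, 29.0% against 28.9% at 0, and 28.8% against 25.7% at −0.5. The sign depends on a correlation nobody has measured.

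**The case against.** The best defence is that little hangs on this comparison. It is exploratory, the trial treats at most 15 people, and Section 1.1 separately lists 1,25D levels and change from baseline over the five days. Individual data may be shown (Section 9.4.8) and mixed models used (Section 9.4.9). All of that stands and limits the consequence. It does not repair the defined comparison, which is the one with a significance threshold attached.

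The size is also soft. It rests on an assumed CV, is negligible for crossings at 10%, and shrinks with day-to-day correlation. Home calcitriol ends shortly before baseline ("All participants will be instructed to stop taking calcitriol and home calcium dosage, with last doses on Day -2"). Any carry-over into Day 1 would raise the baseline and push the change down, partly offsetting the bias. This too stands, but it does not equalise the number of draws.

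A reader might infer three stronger things that the documents do not support.

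- **That the exclusion drops the worst responders and so inflates the result.** Exclusion follows receipt of calcitriol. The early triggers allow an alternative: "cCa < 7 mg/dL, or borderline QT prolongation, would cause investigators to give oral calcium and/or calcitriol". Those managed with oral calcium alone stay in. Those excluded are poor calcium responders, not shown to be poor 1,25D responders, and there is a plain reason to exclude them, since calcitriol is the measured analyte. The rule does condition on a post-dose event, but the direction of any bias is not established.
- **That good calcium responders always get more draws.** Early stopping can cut draws in the strongest responders, so the link is not one-way.
- **That the plan reports an inflated responder rate.** It defines no such rate. The crossing chances above show what the threshold does if applied per participant. The bias in the mean change needs no such reading.

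Averaging the pre-calcitriol draws would remove the bias from taking a maximum. It would still leave precision, and so the crossing chance, dependent on draw count: at CV 20% with independent baseline draws, 1.4% for a mean of three against 4.4% for one.

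**Conclusion.** The point holds for the comparison as written. A maximum of one to four draws against a baseline mean overstates the 1,25D change, and the overstatement varies with a draw count that the participant's own response helps set. With no drug effect, independent noise and independent baseline draws, the mean apparent change is about +0.5% to +5% with one draw and +9% to +32% with three, over an assumed CV of 10% to 30%. From CV 15% upward, the chance of crossing 50% is roughly 2.3 to 2.8 times as high with three draws as with one (27.5/11.8 and 3.4/1.2). Confidence is high on the direction of the maximum-against-mean bias and moderate on its size. No upward bias is claimed from the exclusion. This is worth correcting in an exploratory endpoint; it does not touch the primary or secondary analyses.

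**What to change.** Reword the endpoint in Sections 1.1 and 3:

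1. Main comparison: the Day 3 pre-dose 1,25D, before any calcitriol, against the mean of the two Day 1 pre-dose values.
2. Report how many participants are excluded for earlier calcitriol. Add a sensitivity analysis using their last pre-calcitriol value on encaleret, where one exists; someone given calcitriol on Day 1 may have none. Report separately anyone who stopped encaleret before the Day 3 draw.
3. Show later pre-calcitriol values (Days 4 and 5, and the Day 5 24-hour draw) descriptively by calcitriol status, with the number of draws per participant.
4. Do not apply the 50% threshold to a maximum, and say whether it refers to a participant or to the group.

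The cost is wording. Every sample is already scheduled and no treatment rule changes. The downside is that a rise appearing only on Days 4 or 5 is not counted in the main comparison, which matters in a trial whose stated worry is missing a real effect. Such a rise would remain visible in the 1,25D time course already listed.
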